### 8.3 Toxicity Monitoring

Toxicity will be assessed using NCI CTCAE version 4.03. Subjects will be monitored for excessive toxicity over the duration of the study. A toxicity rate due to the study regimen greater than 35% would be considered unacceptable. Toxicity events that will be monitored will be those that call for discontinuation of therapy, as defined in Section 4.4.

Pocock-type boundaries will be utilized as described in Ivanova, A., et al. Biometrics. 2005; 61(2):540-5. If a toxicity boundary is reached, accrual for the study will be suspended and the Data Safety and Monitoring Committee (DSMC) will be alerted. The DSMC (in consultation with the Principal Investigator and the drug company) will evaluate the toxicity events to help determine whether or not to terminate the study.

Accrual to the trial is to be suspended if the number of protocol defined toxic events is equal to or larger than boundary in the table below.

Number of Subjects	1	2	3	4	5	6	7	8	9	10	11	12	13	14	15	16	17	18	19	20
Boundary	-	-	-	-	5	6	6	7	7	8	9	9	10	10	11	11	12	12	13	13
Number of Subjects	21	22	23	24	25	26	27	28	29	30	31	32	33	34	35	36	37	38	39	40
Boundary	13	14	14	15	15	16	16	17	17	18	18	19	19	19	20	20	21	21	22	22
Number of Subjects	41	42	43	44	45	46	47	48	49	50	51	52	53	54	55	56	57	58	59	60
Boundary	22	23	23	24	24	25	25	26	26	26	27	27	28	28	28	29	29	30	30	31
Number of Subjects	61	62	63	64	65	66														
Boundary	31	31	32	32	33	33														

### 8.4 Data Analysis Plans

ORRs and best response rates will be determined using both the RECIST 1.1 and irRECIST criteria will be reported along with their corresponding 95% confidence intervals. Wilson’s method will be used to calculate confidence intervals for these rates (reported as percentages). PFS and the duration of response estimates using both the RECIST 1.1 and irRECIST criteria will be calculated using the Kaplan-Meier (or product-limit) method. OS will also be calculated using the Kaplan-Meier (or product-limit) method. These time to event estimated functions will be plotted, and median time to estimates will be reported along with their 95%

confidence intervals. The confidence intervals for these time to event functions will be calculated using the standard and well known “loglog” method. If appropriate, 6, 12, and 24 month estimates for the time to event functions will also be reported.

The primary analysis will apply to the total number of evaluable subjects. Toxicity and safety information will be reported in a descriptive manner in the form of frequency tables. Toxicity will be defined through the number and frequency of treatment-emergent grade 3 and 4 toxicities as defined by National Cancer Institute - Common Terminology Criteria for Adverse Events (NCI CTCAE v4.03). Hypothesis generating exploratory analyses will be performed when appropriate sample size considerations allow. The definitions of the outcomes (or endpoints) of interest can be found in section 2.4.

## **9.0 STUDY MANAGEMENT**

### **9.1 Institutional Review Board (IRB) Approval and Consent**

It is expected that the IRB will have the proper representation and function in accordance with federally mandated regulations. The IRB should approve the consent form and protocol.

In obtaining and documenting informed consent, the investigator should comply with the applicable regulatory requirement(s), and should adhere to Good Clinical Practice (GCP) and to ethical principles that have their origin in the Declaration of Helsinki.

Before recruitment and enrollment onto this study, the subject will be given a full explanation of the study and will be given the opportunity to review the consent form. Each consent form must include all the relevant elements currently required by the FDA Regulations and local or state regulations. Once this essential information has been provided to the subject and the investigator is assured that the subject understands the implications of participating in the study, the subject will be asked to give consent to participate in the study by signing an IRB-approved consent form.

Prior to a subject’s participation in the trial, the written informed consent form should be signed and personally dated by the subject and by the person who conducted the informed consent discussion.

### **9.2 Required Documentation**

Before the study can be initiated at any site, the following documentation must be provided to the Clinical Protocol Office (CPO) at the University of North Carolina.

- A copy of the official IRB approval letter for the protocol and informed consent

- IRB membership list
- CVs and medical licensure for the principal investigator and any sub-investigators who will be involved in the study.
- Form FDA 1572
- Financial disclosure
- CAP and CLIA Laboratory certification numbers and institution lab normal values
- Executed clinical research contract

### **9.3 Registration Procedures**

All subjects must be registered with the LCCC CPO Multicenter Office at the University of North Carolina before enrollment to study. To register a subject call the Multicenter office at [[contact]]([contact]) Monday-Friday 8:30 am – 5:00 pm EST. Scan and email the Multicenter Project Manager (preferred) or [contact]) the registration form, signed informed consents, signed eligibility form and all source documents to confirm eligibility. Eligibility may be confirmed by the UNC Study Coordinator for subjects treated at UNC. When sending registration request with eligibility documentation, please allow 24 hours for source to be reviewed.

### **9.4 Data Management and Monitoring/Auditing**

UNC LCCC will serve as the coordinating center for this trial. Data will be collected through a web based clinical research platform, OnCore®. Other study institutions will be given a password to directly enter their own data onto the web site via electronic case report forms (eCRFs). Multicenter personnel will coordinate and manage data for quality control assurance and integrity.

All data will be collected and entered into OnCore® by Clinical Research Associates (CRAs) from UNC LCCC and participating institutions. The investigators at each site will allow monitors to review all source documents supporting data entered into OnCore®. The Multicenter Data Coordinator can be reached at [contact] or [name].

All data will be monitored and source data will be verified on selected subjects. Queries will be issued on an ongoing basis on all subjects. Participating sites should respond to data queries within 14 days of receipt. The LCCC compliance committee or their designee will audit trial sites every twelve months while still enrolling or subjects are still on treatment. Participating sites must send source and regulatory documents to LCCC upon request, for remote monitoring and/or audit review.

### **9.5 Adherence to the Protocol**

Except for an emergency situation in which proper care for the protection, safety, and well-being of the study subject requires alternative treatment, the study shall be conducted exactly as described in the approved protocol.

### 9.5.1 Emergency Modifications

UNC and Affiliate investigators may implement a deviation from, or a change of, the protocol to eliminate an immediate hazard(s) to trial subjects without prior UNC or their respective institution's IRB/IEC approval/favorable opinion.

#### For Institutions Relying on UNC's IRB:

For any such emergency modification implemented, a UNC IRB modification form must be completed by UNC Research Personnel within five (5) business days of making the change.

#### For Institutions Relying on Their Own IRB:

For Affiliate investigators relying on their own institution's IRB, as soon as possible after the modification has been made, the implemented deviation or change and the reasons for it should be submitted to:

- To UNC Principal Investigator for agreement
- The Affiliate institution's IRB for review and approval. (Once IRB's response is received, this should be forwarded to the Multicenter Regulatory Associate).

### 9.5.2 Single Subject/Subject Exceptions

Eligibility single subject exceptions are not permitted for Lineberger Comprehensive Cancer Center Investigator Initiated Trials under any circumstances. Other types of single subject exceptions may be allowed if proper regulatory review has been completed in accordance with Lineberger Comprehensive Cancer Center's Single Subject Exceptions Policy.

### 9.5.3 Other Protocol Deviations/Violations

According to UNC's IRB, a protocol deviation is any unplanned variance from an IRB approved protocol that:

- Is generally noted or recognized after it occurs
- Has no substantive effect on the risks to research participants
- Has no substantive effect on the scientific integrity of the research plan or the value of the data collected
- Did not result from willful or knowing misconduct on the part of the investigator(s).

An unplanned protocol variance is considered a violation if the variance meets any of the following criteria:

- Has harmed or increased the risk of harm to one or more research participants.
- Has damaged the scientific integrity of the data collected for the study.
- Results from willful or knowing misconduct on the part of the investigator(s).
- Demonstrates serious or continuing noncompliance with federal regulations, State laws, or University policies.

If a deviation or violation occurs please follow the guidelines below:

For Institutions Relying on UNC's IRB:

**Protocol Deviations:** UNC or Affiliate personnel will record the deviation in OnCore®, and report to any sponsor or data and safety monitoring committee in accordance with their policies. Deviations should be summarized and reported to the IRB at the time of continuing review.

**Protocol Violations:** Violations should be reported by UNC personnel within one (1) week of the investigator becoming aware of the event using the same IRB online mechanism used to report Unanticipated Problems.

For Institutions Relying on Their Own IRB:

In addition to adhering to the policies regarding protocol compliance set forth by your institution's IRB, the following is also required:

**Protocol Deviations:** In the event a deviation from protocol procedures is identified, record the deviation in OnCore®.

**Protocol Violations:** Any protocol violation that occurs must be reported to your IRB per institutional policies and reported to the Multicenter Project Manager within 5 days. UNC-CH will determine if the violation affects the safety of the subject and integrity of the data. Once your institution's IRB response is received, please forward to the Multicenter Regulatory Associate.

**Unanticipated Problems:**

UNC

Any events that meet the criteria for "Unanticipated Problems" as defined by UNC's IRB must be reported by the Study Coordinator using the IRB's web-based reporting system.

Affiliate Sites:

Any events that meet the criteria for "Unanticipated Problems (UPs)" as defined by UNC's IRB must also be reported to the Multicenter Project Manager. The Multicenter Project Manager will report the event to the UNC IRB using the IRB's web-based reporting system. Examples of such UPs include a lost or stolen laptop computer that contains sensitive study information.

## 9.6 Amendments to the Protocol

Should amendments to the protocol be required, the amendments will be originated and documented by the Principal Investigator at UNC. It should also be noted that when an amendment to the protocol substantially alters the study design or the potential risk to the subject, a revised consent form might be required.

### For Institutions Relying on UNC's IRB:

The written amendment, and if required the amended consent form, must be sent to UNC's IRB for approval prior to implementation.

### For Institutions Relying on Their Own IRB:

Investigators must submit the amendment to their institution's IRB for approval. For multicenter studies, any multicenter site must submit their informed consent revisions to the Multicenter Regulatory Associate prior to submission to their IRB.

## 9.7 Record Retention

Study documentation includes all eCRFs, data correction forms or queries, source documents, Sponsor-Investigator correspondence, monitoring logs/letters, and regulatory documents (e.g., protocol and amendments, IRB correspondence and approval, signed subject consent forms).

Source documents include all recordings of observations or notations of clinical activities and all reports and records necessary for the evaluation and reconstruction of the clinical research study.

Government agency regulations and directives require that all study documentation pertaining to the conduct of a clinical trial must be retained by the study investigator. In the case of a study with a drug seeking regulatory approval and marketing, these documents shall be retained for at least two years after the last approval of marketing application in an International Conference on Harmonization (ICH) region. In all other cases, study documents should be kept on file until three years after the completion and final study report of this investigational study.

## 9.8 Obligations of Investigators

The Principal Investigator is responsible for the conduct of the clinical trial at the site in accordance with Title 21 of the Code of Federal Regulations and/or the Declaration of Helsinki. The Principal Investigator is responsible for personally overseeing the treatment of all study subjects. The Principal Investigator must assure that all study site personnel, including sub-investigators and other study staff members, adhere to the study protocol and all FDA/GCP/NCI regulations and guidelines regarding clinical trials both during and after study completion.

The Principal Investigator at each institution or site will be responsible for assuring that all the required data will be collected and entered into the eCRFs. Periodically, monitoring visits will be conducted, and the Principal Investigator will provide access to his/her original records to permit verification of proper entry of data. At the completion of the study, all eCRFs will be reviewed by the Principal Investigator and will require his/her final signature to verify the accuracy of the data.

## 11.0 APPENDICES

### 11.1 ECOG Performance Status

Grade	Description
0	Normal activity. Fully active, able to carry on all pre-disease performance without restriction.
1	Symptoms, but ambulatory. Restricted in physically strenuous activity, but ambulatory and able to carry out work of a light or sedentary nature (e.g., light housework, office work).
2	In bed <50% of the time. Capable of only limited self-care, confined to bed or chair more than 50% of waking hours.
3	In bed >50% of the time. Capable of only limited self-care, confined to bed or chair more than 50% of waking hours.
4	100% bedridden. Completely disabled. Cannot carry on any self-care. Totally confined to bed or chair.
5	Dead.

\* As published in Am. J. Clin. Oncol.: *Oken, M.M., Creech, R.H., Tormey, D.C., Horton, J., Davis, T.E., McFadden, E.T., Carbone, P.P. Toxicity and Response Criteria of the Eastern Cooperative Oncology Group. Am J Clin Oncol 5:649-655, 1982. The Eastern Cooperative Oncology Group, Robert Comis M.D., Group Chair.*

[figure not shown]
## 11.2 Treatment Algorithms for Nivolumab Therapy

Algorithms are presented for management of GI, renal, hepatic, pulmonary, endocrine, skin and neurological toxicities are provided. NCI-CTCAEv4.03 criteria apply as referenced in the protocol. **The algorithms are potential suggested schemes for management of potential irAEs but should only serve as a complement to investigator judgment and additional guidelines for monitoring and management of immune related toxicities.** Additionally, recommend management referring to NCCN Guidelines “Management of Immune Checkpoint Inhibitor-Related Toxicities.” In cases of discrepancy between the algorithms and additional guidelines, investigator judgment should be used, and highly encourage consultation with medical monitor.

## GI Adverse Event Management Algorithm

[figure not shown]
Rule out non-inflammatory causes. If non-inflammatory cause is identified, treat accordingly and continue I-O therapy. Opiates/narcotics may mask symptoms of perforation. Infliximab should not be used in cases of perforation or sepsis.

Patients on IV steroids may be switched to an equivalent dose of oral corticosteroids (e.g. prednisone) at start of tapering or earlier, once sustained clinical improvement is observed. Lower bioavailability of oral corticosteroids should be taken into account when switching to the equivalent dose of oral corticosteroids.

## Renal Adverse Event Management Algorithm

[figure not shown]
Rule out non-inflammatory causes. If non-inflammatory cause, treat accordingly and continue I-O therapy

Patients on IV steroids may be switched to an equivalent dose of oral corticosteroids (e.g. prednisone) at start of tapering or earlier, once sustained clinical improvement is observed. Lower bioavailability of oral corticosteroids should be taken into account when switching to the equivalent dose of oral corticosteroids.

## Pulmonary Adverse Event Management Algorithm

[figure not shown]
Rule out non-inflammatory causes. If non-inflammatory cause, treat accordingly and continue I-O therapy. Evaluate with imaging and pulmonary consultation.

Patients on IV steroids may be switched to an equivalent dose of oral corticosteroids (e.g. prednisone) at start of tapering or earlier, once sustained clinical improvement is observed. Lower bioavailability of oral corticosteroids should be taken into account when switching to the equivalent dose of oral corticosteroids.

## Endocrinopathy Management Algorithm

[figure not shown]
Rule out non-inflammatory causes. If non-inflammatory cause, treat accordingly and continue I-O therapy. Consider visual field testing, endocrinology consultation, and imaging.

Patients on IV steroids may be switched to an equivalent dose of oral corticosteroids (e.g. prednisone) at start of tapering or earlier, once sustained clinical improvement is observed. Lower bioavailability of oral corticosteroids should be taken into account when switching to the equivalent dose of oral corticosteroids.

## Skin Adverse Event Management Algorithm

Rule out non-inflammatory causes. If non-inflammatory cause, treat accordingly and continue I-O therapy.

[figure not shown]
Patients on IV steroids may be switched to an equivalent dose of oral corticosteroids (e.g. prednisone) at start of tapering or earlier, once sustained clinical improvement is observed. Lower bioavailability of oral corticosteroids should be taken into account when switching to the equivalent dose of oral corticosteroids.

\*Refer to NCI CTCAE v4 for term-specific grading criteria.

^If SJS/TEN is suspected, withhold I-O therapy and refer patient for specialized care for assessment and treatment. If SJS or TEN is diagnosed, permanently discontinue I-O therapy.

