**4.4.2 Nivolumab +/- Ipilimumab Dosing Delays/Dose Modifications**

Toxicity grades per NCI-CTCAE Criteria v 4.03

Adverse Reaction	Severity	Dose Modification
Adrenal Insufficiency f	Grade 2 adrenal insufficiency	Withhold dose a
	Grade 3-4 adrenal insufficiency	Permanently discontinue c
Myocarditis	Grade 3-4 myocarditis	Permanently discontinue
Infusion Related Reaction	Grade 1-2 infusion related reaction	See section 4.5.2 for guidance
	Grade 3-4 infusion related reaction or anaphylaxis	Permanently discontinue
Uveitis, eye pain, blurred vision	Grade 2 that does not respond to topical therapy and does not improve to grade 1 severity within re-treatment period OR requires systemic treatment	Permanently discontinue
	Grade 3-4 uveitis or eye pain or blurred vision	Permanently discontinue
Colitis f	Grade 2 diarrhea or colitis	Withhold dose a
	Grade 3 diarrhea or colitis	Withhold dose a
	Grade 4 diarrhea or colitis	Permanently discontinue
Pneumonitis f	Grade 2 pneumonitis	Withhold dose a
	Grade 3 or 4 pneumonitis	Permanently discontinue
Hypophysitis f	Grade 2 hypophysitis	Withhold dose a
	Grade 3-4 hypophysitis	Permanently discontinue e
Type 1 Diabetes Mellitus f	Grade 3 hyperglycemia	Withhold dose a
	Grade 4 hyperglycemia	Permanently discontinue e
Nephritis and Renal Dysfunction f	Serum creatinine more than 1.5 and up to 6X ULN	Withhold dose a
	Serum creatinine more than 6X ULN	Permanently discontinue
Rash f	Grade 3 rash	Withhold dose a
	Grade 4 rash	Permanently discontinue
Encephalitis f	New-onset moderate or severe neurologic signs or symptoms	Withhold dose a
	Immune-mediated encephalitis	Permanently discontinue
Hepatitis	See section 4.4.2.1 for guidance	
Other f	Other Grade 3 adverse reaction b First occurrence	Withhold dose a
	Recurrence of same Grade 3 adverse reaction	Permanently discontinue
	Life-threatening or Grade 4 adverse reaction d	Permanently discontinue
	Requirement for 10 mg per day or greater prednisone or equivalent for more than 12 weeks	Permanently discontinue
	Persistent Grade 2 or 3 adverse reactions lasting 12 weeks or longer e	Permanently discontinue

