#### **4.4.2.4 Management Algorithms for Immune-related Events for Nivolumab +/- Ipilimumab**

Guidelines for the management of immune-related events can be found in the current Nivolumab Investigator Brochure AND in the approved USPI in the US.

Immuno-oncology (I-O) agents are associated with AEs that can differ in severity and duration than AEs caused by other therapeutic classes. Nivolumab is considered an I-O agent in this protocol. Early recognition and management of AEs associated with immuno-oncology agents may mitigate severe toxicity. Management algorithms have been developed to assist investigators in assessing and managing the following groups of AEs:

For mandatory guidance on dosing of nivolumab and/or ipilimumab with specified immune related adverse events, please refer to section 4.4.2 and

section 4.4.2.1. For additional management, including monitoring and use of corticosteroids or additional immunosuppressant therapies, recommend using guidelines for management of immunotherapy related toxicities, primarily the NCCN Management of Immunotherapy-Related Toxicities Version 1.2020. Section 11.2 has algorithms for possible further management of selected toxicities, but management does not have to follow direction of Section 11.2. Instead, these algorithms are only an additional resource to complement other guidelines and the Investigator's medical judgment.

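### The binding dosing rules contain no diagnosis-based stop for SJS or TEN; the only one is a note in optional Appendix 11.2, which matters if a diagnosed case can be graded 3 and recover

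*Combined protocol and SAP*

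**What the plan says.** **Appendix 11.2, skin algorithm.** Two notes under the figure deal with SJS/TEN. For suspicion: "If SJS/TEN is suspected, withhold I-O therapy and refer patient for specialized care for assessment and treatment". For diagnosis: "If SJS or TEN is diagnosed, permanently discontinue I-O therapy". Grading is sent outside the protocol: "Refer to NCI CTCAE v4 for term-specific grading criteria".

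**Status of Appendix 11.2.** Its introduction says "The algorithms are potential suggested schemes for management of potential irAEs but should only serve as a complement to investigator judgment". Section 4.4.2.4 says "management does not have to follow direction of Section 11.2", and footnote f of Section 4.4.2 (attached to the Rash row) and the liver table in 4.4.2.1 say the same.

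**Where the binding rules are.** Section 4.4.2.4 states: "For mandatory guidance on dosing of nivolumab and/or ipilimumab with specified immune related adverse events, please refer to section 4.4.2", and adds 4.4.2.1. Section 4.4.2.5 then lists criteria for permanent discontinuation.

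**What those rules cover.** Sections 4.4.2, 4.4.2.1 and 4.4.2.5 do not mention SJS or TEN. The Rash row works by grade alone: withhold at Grade 3, stop at Grade 4. The catch-all block withholds for a first "Other Grade 3 adverse reaction" and stops for a "Life-threatening or Grade 4 adverse reaction".

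**Recognised risk.** Section 5.2.8 lists fatal TEN, described as rare, among the severe rashes seen with nivolumab. It attaches no dosing rule.

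**The concern.** Permanent discontinuation is a dosing rule, and the protocol assigns dosing rules to Section 4.4.2. Appendix 11.2 is introduced for additional management, such as monitoring and immunosuppression. An instruction to stop on diagnosis, placed only in the appendix, does not bind a site. If a diagnosed case can fall into a grade for which the table says withhold and later resume, the table permits re-treatment where the protocol's own note advises stopping. What is at stake is the safety of an individual patient after a reaction type that the protocol acknowledges can be fatal. No efficacy inference is involved.

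**Working it through.** No published figure is in dispute, so the check traces a diagnosed case through each rule.

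**Branch A: every diagnosed case is Grade 4 or life-threatening.** The Rash row (Grade 4), the catch-all block (Grade 4 or life-threatening) and the Grade 4 bullet in 4.4.2.5 stop treatment. There is no gap.

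**Branch B (assumption): a diagnosed case can be graded 3.**

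1. *Initial action.* The Rash row at Grade 3, or the first-occurrence catch-all row, says withhold.
2. *Stops that still apply.* Treatment ends permanently if any of these holds:
   - the case is classed as a Grade 3 hypersensitivity reaction, of any duration (4.4.2.5);
   - it is a recurrence of the same Grade 3 reaction under the catch-all block (4.4.2);
   - it needs prednisone at 10 mg/day or more for over 12 weeks (4.4.2);
   - it persists at Grade 2 or 3 for 12 weeks or longer (4.4.2);
   - the toxicity lasts beyond 6 weeks (4.4.2 footnote a). Section 4.4.2.5 has its own stop for interruptions beyond 6 weeks, with exceptions that include prolonged steroid tapers.
3. *A stop that does not apply.* The 4.4.2.5 rule for Grade 3 events lasting over 7 days is limited to non-skin events.
4. *Resumption.* Footnote a says treatment resumes once the reaction is back to Grade 0 or 1. Section 4.4.2.3 permits the same at Grade 1 or below, or baseline, with no SJS/TEN exception.
5. *Timing.* 6 weeks × 7 = 42 days, which matches the 8-42 day delay in 4.4.2.3.1. That section only fixes which visit to use once the resume criteria are met; it gives no permission of its own.
6. *What remains before restart.* Section 4.4.2.5 has a stop if the investigator sees substantial risk, an instruction to weigh the safety of resuming, discussion with the medical monitor (written at least for choices such as dropping one agent), and use of rechallenge guidelines. None is triggered by the diagnosis itself, and the documents do not show what those guidelines say on SJS/TEN.

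**The suspicion half.** This is largely covered already. Grade 3 rash is withheld, 4.4.2.2 allows a hold on investigator judgment, and 4.5.1 recommends dermatology referral at Grade 3 or 4. The missing part is the stop on diagnosis.

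**Comparison within the table.** Section 4.4.2 withholds for new moderate or severe neurologic signs and stops permanently for immune-mediated encephalitis, without reference to grade. A diagnosis-based row therefore fits the existing format.

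**Effect on Section 8.3.** The events monitored there are those that call for discontinuation under Section 4.4. The boundary is 19 at 32 subjects and 29 at 56. One additional event is 1/19 = 5.3% or 1/29 = 3.4% of the boundary, which is negligible.

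**The case against.** The strongest objection is that the gap depends on a source the documents do not contain. If CTCAE places every diagnosed case at Grade 4, or every such case is judged life-threatening, nothing is missing. This stands, and the point is conditional on it.

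Second, the instruction in 11.2 is a note to a figure that is not visible here. It may attach only to the boxes for severe grades. A reader might infer that the sponsor has already ruled out re-treatment at every grade. The documents do not support that: the legible text states no grade limit, but its anchor cannot be seen, and the appendix describes itself as suggestion.

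Third, the safeguards are real. Those in 4.4.2.5 are in the body of the protocol and address events that miss a mandatory stop. Section 7.3.2 requires the medical monitor to be told of every serious adverse event within 24 hours, and a diagnosed case would plausibly qualify under 7.1.4. The steroid taper of at least one month in 4.5.3 makes a restart within 42 days less likely. All this narrows the gap. It does not close it, because notification, deliberation and judgment are not a rule to stop.

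Fourth, the optional status of 11.2 looks deliberate, since it is repeated in several places in favour of named outside guidelines. That explains why management advice is optional. It does not explain why a dosing stop is found only there.

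Finally, Section 4.4.1 would still let panitumumab restart at the original dose after a first Grade 3 dermatologic reaction improves to below Grade 3, so the change protects only against nivolumab with or without ipilimumab. That is correct; the 11.2 note also concerns only immuno-oncology therapy.

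**Conclusion.** The point holds in a narrow, conditional form. The mandatory dosing rules have no diagnosis-based stop for SJS or TEN. The exposed case is one that is diagnosed, graded 3, not life-threatening, not classed as hypersensitivity, not a recurrence, free of prolonged steroid need, and back to Grade 0-1 within 6 weeks. For that case the table permits resumption, and only discretionary safeguards remain.

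A reader might go further and infer that the protocol directs re-treatment after SJS/TEN, or leaves such cases generally unprotected. Neither follows: the Grade 4 and life-threatening stops, the hypersensitivity stop, the time limits and the 4.4.2.5 safeguards all apply. Nor does the omission distort safety monitoring to any useful degree.

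The key assumption is that a diagnosed case can be graded below 4. The documents give no rate for SJS or TEN, so no frequency is claimed. Sample size, error rates and decision rules are untouched. This is an inexpensive improvement to individual patient safety.

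**What to change.** Add one row to the table in Section 4.4.2 and a matching bullet to Section 4.4.2.5:

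*SJS/TEN suspected: withhold nivolumab +/- ipilimumab. SJS or TEN diagnosed: permanently discontinue, any grade.*

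The words *any grade* are proposed as the safe wording; the appendix figure does not prove them. If every diagnosed case is in fact Grade 4 or life-threatening, the row merely restates what already happens. Once in Section 4.4, the event counts under Section 8.3 with no further edit.

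The cost is one table row and one bullet, with no extra patients, procedures or analyses.
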